2. RATIONALE

Current evidence indicates that the risk of severe COVID-19 illness increases with age, male gender and with certain chronic medical problems such as arterial hypertension, cardiovascular disease, chronic lung disease, obesity and diabetes. Whether or not PLWHIV on treatment with a normal CD4 cell count and suppressed HIV-RNA are at an increased risk of serious illness or death, many will have other conditions that increase their risk. Indeed, almost half PLWH in Europe are older than 50 years and chronic medical conditions, including cardiovascular and chronic lung disease, are more common in PLWHIV.

Case series of PLWHIV with COVID-19 from China, Spain, Germany, Italy and the United States [10-22] show no clear evidence for a higher COVID-19 infection rate or different disease course in people with and without HIV. Of note, most case series of PLWHIV report a younger age in their study population than in HIV-negative hospitalised COVID-19 patients, but comparable rates of comorbidities. A cohort study from the United Kingdom reported a small potential increase in the risk of mortality among PLWHIV once hospitalised with COVID-19, albeit with no data around the risk of developing severe COVID-19 or hospitalisation among this cohort in the first place and no data on antiretroviral therapy (ART), viral load (VL) or CD4 count [23].

An analysis of risk factors for COVID-19 deaths in the Western Cape [24] described after adjusting for other risk factors that HIV increased a COVID-19 patient's death risk by a factor of 2.14 (95% CI 1.70;2.70), and active TB by a factor of 2.70 (95% CI 1.91-4.04). Finally, Spanish researchers described the incidence of COVID-19 and risk of hospitalization among 77,590 PLWHIV receiving ART [7]. During a 3-month period, 236 PLWHIV were diagnosed with COVID-19, and 151 were hospitalized. The risk of hospitalization by NRTI treatment per 10,000 persons was lowest for TDF/FTC (10.5), while other NRTI strategies were similar.

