6.2 Data collection

Only real-world retrospective data will be used for this study. Deidentified retrospective data will be transcribed into the eCRF system from source data at each clinical site or from existing COVID-19 cohort databases, where appropriate. No personal identifiable data will be transmitted to NEAT ID. The data elements will be transcribed from source data according to the data collection list below. Mechanisms to ensure data quality and integrity will be deployed as per applicable standard operating procedures and in line with GCP and GPP. Patients and controls will be identified and documented by participating sites, provided unbiased matching for inpatient/outpatient status at the time of COVID-19 diagnosis is ensured. Alternatively, and to avoid potential site-related bias during selection of HIV negative controls with COVID-19 diagnosed in hospital, data from matched controls will be obtained from appropriate existing COVID-19 cohort databases, e.g. LEOSS (Lean European Open Survey on SARS-CoV-2 infected patients) or ISARIC (International Severe Acute Respiratory and emerging Infection Consortium).

For all patients the following information will be collected:

- Age
- Sex
- Ethnicity (where available)
- Comorbidities (see appendix 1)
- Weight (kg) and height (m) (to calculate BMI)

For patients with COVID-19 the following information will be collected (where applicable):

- Date of positive PCR test result (documented or patient-reported)
- COVID-19 diagnosis inpatient or outpatient
- All-cause mortality in hospital, or palliative discharge, or mortality at 6 weeks after diagnosis of COVID-19 or at discharge from hospital
- Hospitalisation for COVID-19 and length of hospitalisation
- Critical care admission (high dependency unit or intensive care unit) for COVID-19 and length of stay in critical care
- Length of invasive ventilation
- Length of extracorporeal membrane oxygenation (ECMO)
- Need for kidney replacement therapy
- Inflammatory markers and blood cell counts at COVID-19 diagnosis¹ (if available):
 - Full blood cell count (Platelet count, RBC Count, WBC count (absolute), Haemoglobin, Haematocrit, MCV, MCH, Neutrophils, Lymphocytes, Monocytes, Eosinophils, and Basophils), ALT, AST, total bilirubin, urea, serum creatinine, calcium, glucose and HbA1C levels, total cholesterol, triglycerides, CRP, D-dimer, ferritin, and lactate dehydrogenase

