7.3.2 Primary outcome analysis

The first primary outcome analysis will be performed on PLWHIV with COVID-19 versus HIV uninfected individuals with COVID-19. The endpoint is the occurrence of critical care admission (high dependency unit or intensive care unit), mortality in hospital or palliative discharge when discharged from hospital, or mortality at 6 weeks after diagnosis of COVID-19 or at discharge from hospital (where applicable). Kaplan-Meier estimates will be used to estimate the proportion of participants with the primary endpoint events. Unadjusted and adjusted hazard ratios (HR) will be estimated using the Cox proportional hazard model to assess the impact of HIV-infection on the severity of COVID-19. The validity of the proportionality assumption will be assessed and tested. The adjusted variables will be the following (potential confounders): Age (<60 vs 60-64 vs 65-69 vs 70-74 vs ≥75 years); Sex at birth (female vs male); Obesity (BMI>30 kg/m²); and Comorbidities (see appendix 1).

The second primary outcome analysis will be performed within the group of PLWHIV (PLWHIV with COVID-19 versus PLWHIV without COVID-19). The endpoint is to assess factors associated with severe COVID-19 within the group of PLWHIV. Conditional logistic regression models will be used to account for the case-control matching. The following variables will be assessed: Age (<60 vs 60-64 vs 65-69 vs 70-74 vs ≥75 years); Sex at birth (female vs male); Obesity (BMI >30 kg/m²); Comorbidities (see appendix 1); time since HIV diagnosis (years); current ART; CDC disease stage; CD4 cell nadir; last CD4 cell count/HIV-RNA before COVID-19 diagnosis (including CD4% and CD4/CD8 ratio) at baseline. For continuous variables, the decision to treat the variable as a continuous or categorical variable (as tertile) will be based on the lowest Akaike information criterion value for the corresponding univariable conditional logistic regression analysis. Variables achieving P < 0.20 in the univariable analysis will be retained for the multivariable analysis.

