7.3.3 Secondary outcome analysis

All secondary outcome analysis will be performed on PLWHIV with COVID-19 compared to HIV uninfected individuals with COVID-19.

The proportion of hospitalised patients for COVID-19, the length of stay in hospital, the length of stay on ICU, the length of extracorporeal membrane oxygenation (ECMO), and the proportion of participants with a need for kidney replacement therapy will be estimated using the Kaplan-Meier estimate. Unadjusted and adjusted hazard ratios (HR) will be estimated using the Cox proportional hazard model to assess the impact of HIV-infection on the severity of COVID-19. The adjusted variables will be the same as those used for the first primary outcome analysis.

The number of ventilator-free days (VFDs) will be compared between groups using competing risk regression, with extubation and mortality a competing event, adjusted for potential confounders.

Linear regression models will be used to compare Charlson Comorbidity Index (CCI), the age-adjusted CCI (ACCI), 30-day mortality index after COVID infection, inflammatory marker and blood cell counts at COVID-19 diagnosis between the 2 groups, adjusted for potential confounders. The sample size will be quite large to consider CCI, 30-day mortality index, inflammatory marker and blood cell counts as normally distributed variables.

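### Age enters the adjusted models with everyone under 60 in one band, and BMI as a single cut at 30, although finer values appear to be available; a spline for age and a continuous BMI term would reduce residual confounding at almost no cost

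*Combined protocol and SAP*

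**What the plan says.** Section 7.3.2 gives the age term of the first primary Cox model as follows: "The adjusted variables will be the following (potential confounders): Age (<60 vs 60-64 vs 65-69 vs 70-74", with a last band from 75 years. It gives the BMI term as "Obesity (BMI>30 kg/m²". Sex at birth and the Appendix 1 comorbidities complete the set. The second primary analysis lists the same age bands and BMI cut among its candidate factors. For the secondary Cox models, section 7.3.3 states: "The adjusted variables will be the same as those used for the first primary outcome analysis".

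No reason is given for the cut points, and no analysis with continuous age or BMI is planned. Section 7.3.2 does have a rule that chooses between a continuous form and tertiles by AIC. It is written for the second primary analysis only, and age and obesity are already listed there as fixed categories.

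On the data side, section 6.2 lists age and "Weight (kg) and height (m) (to calculate BMI". Section 4.1 matches both control groups to cases on age within 5 years, which requires near-exact age. BMI is not a matching factor.

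On the population, section 2 says "almost half PLWH in Europe are older than 50 years", and that "most case series of PLWHIV report a younger age in their study population than in HIV-negative hospitalised COVID-19 patients".

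**The concern.** Section 2 names age as a driver of severe COVID-19. With one band below 60, the model treats a 20-year-old and a 59-year-old as the same age. Any age difference below 60 that the design has not removed stays in the estimate.

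What is at stake differs between the two primary questions:

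- **HIV-positive versus HIV-negative.** The residual is whatever age difference survives the 5-year caliper. If controls tend to be the older member of the set, which section 2 makes plausible for hospitalised patients, the HIV effect is understated.
- **Risk factors for severity among PLWHIV.** Cases are matched to controls, not to each other. If severe and non-severe cases are compared, the age term is the only direct control for age. CD4 nadir, time since HIV diagnosis and comorbidity may all vary with age, so leftover age confounding could be read as their effect.

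**Working it through.** **The plan's own figures.** The documents give no figure for the age adjustment. The nearest numbers are the powers in Table 1, and they reproduce with Freedman's log-rank formula for 500 cases and 1500 controls. For ICU at HR 1.4, the case event rate is 1 − 0.85^1.4 = 0.2035. Expected events are 500 × 0.2035 + 1500 × 0.15 = 326.7. Then z = √(326.7/3) × 0.4/(1 + 1.4/3) = 2.85, and power is Φ(2.85 − 1.96) = 81% (stated: 81%). The other three come to 90.8%, 86.2% and 85.4% (stated: 90%, 86%, 85%). These powers do not depend on how age is coded.

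**Share under 60 (assumed distributions).** The documents give only the share over 50. For normal ages, the share under 60 is Φ((60 − mean)/SD):
- mean 49, SD 10 (46% over 50): Φ(1.10) = 86%
- mean 49.5, SD 12 (48% over 50): Φ(0.875) = 81%
- mean 50, SD 13 (50% over 50): Φ(0.77) = 78%

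With mean 49.5 and SD 12, the five bands leave about 46% of the age variance unexplained, and the SD of age inside the under-60 band is about 9 years.

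**First primary comparison.** Assumptions: true HIV HR = 1; case ages normal (49.5, SD 12); 500 cases and 1500 controls; 42 days of follow-up; daily hazard λ(a) = [−ln(1 − 0.15)/42] × r^((a − 49.5)/10), with r from 1.5 to 2.5 per 10 years. Expected events and person-time at each age go into a Poisson model with an HIV term and either the five bands or linear age. Matched sets are not modelled, because the plan does not say that the Cox model accounts for them. Matched controls come from pools with mean age 49.5 to 65.

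| Control ages | HR with bands, all ages | HR with bands, under 60 | HR with linear age |
|---|---|---|---|
| Matched within 5 years | 0.975-0.995 | 0.95-0.99 | 1.00 |
| Every control exactly 5 years older | 0.91-0.94 | 0.83-0.91 | 1.00 |
| Unmatched, about 10 years older | 0.89-0.94 | 0.82-0.91 | 1.00 |

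Under 60, the banded and unadjusted HRs are identical, because the age term is constant there. In the unmatched row the HR without any age term is 0.43-0.65, so the bands remove most of the bias across the whole sample. The value of 1.00 for linear age holds by construction, since the assumed age effect is log-linear.

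**Severe versus non-severe among PLWHIV.** Assumptions: mean age 49.5, SD 11 or 12; severity OR 1.5 or 2.0 per 10 years; low-nadir OR 1.4 per 10 years; 35-40% with low nadir and 15-18% severe at the mean age; true nadir OR = 1. Severity is regressed on low nadir plus the age term, using exact expected proportions.

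| SD | Severity OR per 10 years | Nadir OR, no age term | Nadir OR, bands | Log-OR confounding left |
|---|---|---|---|---|
| 11 | 1.5 | 1.17 | 1.07 | 42-44% |
| 11 | 2.0 | 1.28 | 1.10-1.11 | 39-42% |
| 12 | 1.5 | 1.20 | 1.07 | 38-40% |
| 12 | 2.0 | 1.33-1.34 | 1.11-1.12 | 36-38% |

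With linear age the OR is 1.00 throughout. Repeated simulations under the same kind of inputs gave 1.06-1.12, which is the range used here.

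With 500 cases, the standard error of the log OR is about 0.26. The bias is therefore ln(1.06)/0.26 = 0.22 to ln(1.12)/0.26 = 0.44 standard errors. That moves a nominal 5% two-sided error rate to about 5.5-7%.

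**The case against.** The strongest reply is that the design already deals with most of this. HIV-negative controls are matched on age within 5 years, and the remaining bias of 0.5-2.5% is trivial beside the hazard ratios of 1.4-1.6 that section 7.1 says are detectable for ICU, ventilation and death. This stands for the first primary analysis. The 6-9% figure needs every control at the older edge of the caliper.

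A second reply is that the second primary analysis, read literally, compares PLWHIV with and without COVID-19 in age-matched sets by conditional logistic regression, so age is held within the caliper there too. This also stands for that model. But section 7.3.2 gives the endpoint as severe COVID-19, and primary objective 2 asks about severity. The literal contrast does not answer that question. The mismatch is a separate matter; the 1.06-1.12 applies only to a severity comparison among PLWHIV with COVID-19.

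Third, five-year bands above 60 are not wasted. Under the same assumptions, the 17-19% aged 60 or over supply roughly 27-40% of severe events. This is fair, and it is a reason to keep detail at older ages as well as adding it below 60.

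A reader might infer that the adjustment does almost nothing for most PLWHIV. The documents do not support that. Only the age term is inert, and only within the under-60 band. Sex, obesity and comorbidity terms still act there. Across all ages, the bands remove about 56-64% of the simulated nadir confounding. Nor does the inference carry over to BMI, whose binary term acts at every age.

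**Conclusion.** The point holds as a cheap improvement, not as a flaw that threatens the main result. The coding is as described, the documents give no reason for it, and the age term makes no adjustment among those under 60, who are probably most PLWHIV.

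For the HIV comparison the consequence is small. For a severity comparison within PLWHIV it is modest: a spurious nadir OR of about 1.06-1.12, well under half a standard error with 500 cases. The direction follows if low nadir and severity both rise with age. The size rests on assumptions the documents do not supply: the age distribution, the age gradients, the prevalence of low nadir and the severity rate. Other covariates correlated with age could absorb part of it.

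For BMI, the finding is limited to lost information on a factor that matching does not cover. No bias was estimated.

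**What to change.** In sections 7.3.2 and 7.3.3, enter age as a restricted cubic spline and BMI as a continuous term in the adjusted models. A spline does not rely on the log-linear age effect assumed in the calculations above. Keep the five age bands and the obesity category for descriptive tables and for a sensitivity analysis. State explicitly that the AIC rule does not override this choice.

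The cost is SAP wording and a few extra model terms; age, weight and height are already on the collection list. One check comes first. Section 6.2 allows HIV-negative controls to come from existing cohort databases and does not say in what form these record age. Confirm that they supply age in years. If they do not, use finer bands below 60.

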5.1 Inclusion Criteria

- Cases (PLWHIV + COVID-19)
 - Any gender
 - At least 18 years of age
 - Documented HIV-1 infection
 - Confirmed SARS-CoV-2 infection by documented, or patient-reported, positive result on PCR testing of a nasopharyngeal or respiratory sample, before 1st April 2021

Each case should be matched to a control (1:1 or 1:3 respectively for COVID-19 controls and 1:2 for PLWHIV controls) according to the matching criteria set out in section 4.1.

- Controls (COVID-19)
 - Any gender
 - At least 18 years of age
 - No documented HIV-1 infection
 - Confirmed SARS-CoV-2 infection by documented, or patient-reported, positive result on PCR testing of a nasopharyngeal or respiratory sample, before 1st April 2021
 - Meet the matching criteria
- Controls (PLWHIV)
 - Any gender
 - At least 18 years of age

- Documented HIV-1 infection
- No evidence of SARS-CoV-2 infection
- Meet the matching criteria

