7.3 Statistical analysis plan

The statistical hypotheses are: 1) to show whether HIV infection is associated with severe COVID-19 compared to HIV uninfected individuals; 2) and to identify factors associated with severe COVID-19 within HIV infected population. All eligible subjects with a matching individual will be included in the analysis population (full population analysis).

Time-to-event methods, including Kaplan–Meier survival curves and Cox proportional-hazards models, will be used to compare PLWHIV with COVID-19 versus HIV seronegative COVID-19 controls for the severity of COVID-19 using parameters collected and adjusted for potential confounders. Conditional logistic regression models will be used to assess factors associated with COVID-19 within the group of PLWHIV to account for the case-control matching.

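### The HIV-versus-HIV-negative Cox models adjust for AIDS, which controls cannot have; entered as its own term, it turns the adjusted HR into one for HIV without AIDS

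*Combined protocol and SAP*

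**What the plan says.** Section 7.3 sets the first hypothesis: "to show whether HIV infection is associated with severe COVID-19 compared to HIV uninfected individuals". Section 7.3.2 fits unadjusted and adjusted Cox models "to assess the impact of HIV-infection on the severity of COVID-19". It introduces the covariates with "The adjusted variables will be the following (potential confounders") and lists age bands, sex at birth, obesity "and Comorbidities (see appendix 1"). Appendix 1 includes AIDS as a row, and no section exempts it. The COVID-19 controls must have "No documented HIV-1 infection" (section 5.1).

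For the secondary Cox models, section 7.3.3 states: "The adjusted variables will be the same as those used for the first primary outcome analysis". A later paragraph of 7.3.3 begins "Linear regression models will be used to compare Charlson Comorbidity Index (CCI), the age-adjusted CCI (ACCI), 30-day mortality index after COVID infection" and ends "blood cell counts at COVID-19 diagnosis between the 2 groups, adjusted for potential confounders", without saying which variables those are. The plan does not say whether comorbidities enter as separate terms, a count, an any/none indicator or a score.

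**The concern.** A confounder must be able to affect both exposure and outcome. AIDS follows from HIV and is zero for every control by design, so adjusting for it removes part of the contrast that the model is meant to measure. The adjusted HR will be read as the answer to hypothesis 1. If AIDS raises the risk of severe COVID-19, that excess is left out. Section 3 itself hypothesises that advanced immunodeficiency, defined by CD4 count or nadir, worsens outcomes in PLWHIV. HIV and AIDS are not collinear, so software would fit the model without warning.

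The CCI and ACCI comparisons (secondary endpoint 7) raise a related question. The only list in the plan labelled as potential confounders contains the Appendix 1 items. Those items are also the only comorbidity data collected (section 6.2), so the index has to be built from them.

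**Working it through.** **The plan's own figures.** Table 1 is not in dispute. Freedman's log-rank formula is power = Φ(√(D·r)·(HR−1)/(1+r·HR) − 1.96), with r = n₁/1500 and D = 1500p + n₁(1−(1−p)^HR). It matches every cell within 2 points. For ICU (p = 0.15, HR 1.4, n₁ = 500) it gives 81.2% against the stated 81%.

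**Algebra of a separate AIDS term.** Write log hazard = β₁·HIV + β₂·AIDS + other terms. AIDS = 1 implies HIV = 1, so there are three groups: HIV-negative (0), HIV without AIDS (β₁) and HIV with AIDS (β₁+β₂). The reported HIV HR, exp(β₁), compares HIV without AIDS with HIV-negative at any AIDS prevalence. The HIV-with-AIDS contrast is recoverable as β₁+β₂, but the plan does not say that it will be reported.

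**Approximate size.** Let p be the AIDS share and h the AIDS hazard ratio, neither of which is in the documents. At low event risk the overall HIV HR is about exp(β₁)·[1+p(h−1)], so the separate term lowers it by 1 − 1/[1+p(h−1)]:
- p = 0.25, h = 1: 0%
- p = 0.15, h = 1.5: 1 − 1/1.075 = 7%
- p = 0.25, h = 2: 1 − 1/1.25 = 20%
- p = 0.35, h = 3: 1 − 1/1.70 = 41%

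**Simulation.** Cases: 500. The dashboard's 436/1,187 = 36.7% hospitalised is used as a proxy for inpatient diagnosis. That gives 184 inpatient and 316 outpatient cases, hence 184 + 3×316 = 1,132 controls. Assumed: 42 days, control event risk about 13%, inpatient hazard ×4, obesity 20% with HR 1.3, fifteen other items at 4–10% each with HR 1.4, and HR 1.2 for HIV without AIDS. Results for p = 0.25, h = 2:

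| AIDS coding | Model; other comorbidities | HIV HR, AIDS left out | HIV HR, AIDS in | Change |
|---|---|---|---|---|
| Own term | stratified; equally common | 1.47 | 1.20 | −18.4% |
| Own term | stratified; 1.5 times as common in cases | 1.48 | 1.20 | −18.9% |
| Own term | unstratified; equally common (two runs) | 2.00; 2.02 | 1.65; 1.68 | −17.5%; −16.8% |
| Count | stratified; equally common | 1.47 | 1.34 | −8.8% |
| Count | stratified; 1.5 times | 1.48 | 1.33 | −10.1% |
| Any/none | stratified; equally common | 1.46 | 1.39 | −4.8% |
| Any/none | stratified; 1.5 times | 1.59 | 1.53 | −3.8% |

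Stratified means by inpatient status, which section 7.3.2 does not specify. Without it, inpatients are 184/500 = 36.8% of cases but 184/1,132 = 16.3% of controls, which pushes every HR up. The absolute HRs therefore carry no weight; the relative change from a separate term is similar in both versions. The count and any/none figures come from the stratified version only.

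Over p = 15–35% and h = 1.0–3.0, the separate term changes the HR by between 0 and −37% (1.20/1.91). A count lowers it by 5% (1.22/1.29) to 16% (1.60/1.90), and any/none by 1.5% (1.34/1.36) to 8% (1.74/1.89). With h = 1 a separate term gives no bias but a standard error 8–9% larger (0.149/0.137; 0.146/0.135). A count still lowers the HR by about 8% (1.11/1.21), because it gives AIDS the average hazard of the other items.

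**CCI.** CCI is a weighted sum Σwⱼxⱼ. Regressed on HIV plus every xⱼ at its scored level, the fit is perfect and the HIV coefficient is exactly 0. The documents give no weights, so AIDS weights of 1, 3 and 6 were tried. The crude differences were 2.03, 2.47 and 3.14, and the adjusted HIV coefficient was 0 each time (order 10⁻¹⁴). Dropping only AIDS from the covariates left 0.22, 0.67 and 1.33, which is the AIDS contribution and not the difference in burden. With coarser coding (yes/no items, count, any/none) the coefficient is attenuated by an amount that depends on the assumed weights. For ACCI it is close to zero at scored levels, since the age bands need not match the index.

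**The case against.** The strongest reply is that the plan leaves the coding open. Under any/none coding, or if AIDS carries no excess hazard and enters as its own term, little or nothing changes. That stands, and it is why the effect is stated conditionally. It does not make AIDS a confounder, and the silence leaves the coding to be chosen after the data are seen.

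A second reply is that the unadjusted HR is also planned. It contains no AIDS term, but the groups are not matched on obesity or comorbidity. Section 2 is mixed on whether comorbidity differs: more chronic disease in PLWHIV, yet similar rates in case series of younger patients. The unadjusted HR is therefore not a safe substitute.

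Third, the 15% missingness rule in section 7.5 might happen to drop AIDS. That would be chance, not a planned exclusion.

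On CCI the objection has more force. The sentence reusing the primary covariates sits in the Cox paragraph, and the linear-regression paragraph does not repeat it. An exact zero also needs items entered individually at scored levels, and a perfect fit would be noticed. Secondary objective 3 is descriptive and is served by the tables of section 7.3.1.

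A reader might infer that the plan guarantees a biased primary HR, say 1.20 where 1.47 is true, or a null CCI comparison. The documents support neither. They fix no coding, AIDS share or AIDS hazard, that pair of HRs comes from a stratified model the plan does not specify, and the CCI covariates are undefined.

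**Conclusion.** The concern holds for the Cox models and should be fixed. As written, the adjustment set of every HIV-versus-HIV-negative Cox model includes a consequence of HIV that is absent from controls by design. With a separate term, the adjusted HR answers a narrower question than hypothesis 1, and this follows from algebra alone. The size is illustrative: at an assumed 25% share and doubled hazard, about 17 to 19% lower with a separate term, 9 to 10% with a count and 4 to 5% with any/none. Confidence in the text and direction is high, given some AIDS excess hazard; the percentages are only as good as the assumptions.

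The CCI and ACCI point is conditional and held with lower confidence. If the undefined covariates mean the 7.3.2 list, the models condition on components of their own outcome.

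**What to change.** - In 7.3.2 and 7.3.3, remove AIDS from the adjustment set of every HIV-versus-HIV-negative model. If the split is of interest, also report HIV with AIDS and HIV without AIDS as labelled contrasts beside the overall HR.
- Keep AIDS in the within-PLWHIV analysis.
- State how the remaining comorbidities are coded.
- Give the linear regressions their own covariate list: CCI and ACCI not adjusted for Appendix 1 items, and ACCI not adjusted for age.
- Do not call the resulting HR a total HIV effect. Other Appendix 1 conditions may also follow from HIV, and the groups are matched on inpatient or outpatient status at diagnosis.

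The cost is SAP wording only; no change to data collection is needed.

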3. OBJECTIVES AND OUTCOME MEASURES/ENDPOINTS

It is hypothesised that HIV infection is a risk factor for more severe COVID-19 outcomes and that advanced immunodeficiency as defined by current CD4 T-cell count or CD4 T-cell nadir is a risk factor for more severe COVID-19 outcomes in PLWHIV.

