3.1 Primary objective

1. To describe outcomes of COVID-19 in PLWHIV in comparison to HIV seronegative COVID-19 controls.
2. To identify risk factors (e.g. CD4 cell nadir, current CD4 count, co-morbidities) for severe COVID-19 outcomes within the group of PLWHIV.

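### The second primary analysis is labelled as finding factors for severe COVID-19 in PLWHIV, but it models having COVID-19 at all, so primary objective 2 has no analysis that answers it

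*Combined protocol and SAP*

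**What the plan says.** The target is severity within PLWHIV, and the protocol states it repeatedly.

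- Section 3 hypothesises that "advanced immunodeficiency as defined by current CD4 T-cell count or CD4 T-cell nadir is a risk factor for more severe COVID-19 outcomes in PLWHIV".
- Primary objective 2 in section 3.1 is "To identify risk factors (e.g. CD4 cell nadir, current CD4 count, co-morbidities) for severe COVID-19 outcomes within the group of PLWHIV".
- The second statistical hypothesis in section 7.3 is "to identify factors associated with severe COVID-19 within HIV infected population".
- Section 7.3.2 says of the second primary analysis: "The endpoint is to assess factors associated with severe COVID-19 within the group of PLWHIV".

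The model is something else. Section 7.3.2 defines the comparison as "PLWHIV with COVID-19 versus PLWHIV without COVID-19", fitted by conditional logistic regression on the 1:2 matched sets. Section 5.1 requires of these controls "No evidence of SARS-CoV-2 infection". Section 7.3 describes the same model without the word severe: "Conditional logistic regression models will be used to assess factors associated with COVID-19 within the group of PLWHIV to account for the case-control matching". Section 7.1 sizes it as a search for factors associated with SARS-CoV-2 infection.

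On the remaining analyses, section 7.3.3 states: "All secondary outcome analysis will be performed on PLWHIV with COVID-19 compared to HIV uninfected individuals with COVID-19".

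**The concern.** The uninfected controls have no COVID-19 severity, and the cases enter the model whether severe or not. The coefficients therefore describe who becomes a diagnosed case. If they are reported under the endpoint sentence of 7.3.2, factors for diagnosis will be read as factors for severity.

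The error can run in either direction. A real severity factor that does not affect infection can be missed. A factor that only raises exposure or the chance of being tested can appear as a severity factor. The hypothesis on current CD4 count and nadir would be left without a test.

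**Working it through.** **1. Is severity within PLWHIV analysed anywhere else?**

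- First primary analysis (7.3.2): Cox model, PLWHIV versus HIV-negative patients. It adjusts for age, sex, obesity and comorbidities, with no CD4 count, nadir, ART or HIV-RNA.
- Second primary analysis (7.3.2): PLWHIV with versus without COVID-19.
- Secondary analyses (7.3.3): all PLWHIV versus HIV-negative.

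None compares severe with non-severe disease among PLWHIV. Taking severe COVID-19 as the outcome within the matched sets does not help. Sets with a non-severe case would have no outcome variation and would drop out, and the rest would compare severe cases with uninfected people.

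**2. The plan's own figure.** Section 7.1 uses n = 100 + 50i. With n = 1,500, i = (1,500 - 100)/50 = 28, as stated. (The text there gives 1,500 controls within a total of 1,500. The synopsis figure of 1,000 controls fits the total and the result of 28.) This figure belongs to the infection model. Among the 500 cases the same rule gives (500 - 100)/50 = 8. Table 1 concerns PLWHIV versus HIV-negative patients, so no power statement covers objective 2.

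**3. Assumed severity range.** The composite rate in PLWHIV is not given. From the HIV-negative rates in 7.1 (ICU 15%, death 11%), the union lies between max(0.15, 0.11) = 15% and 0.15 + 0.11 = 26%, before high dependency admission and palliative discharge. At the plan's upper hazard ratio of 2 this becomes 1 - 0.85² = 27.8% to 1 - 0.74² = 45.2%. I take 10% as the low end; section 6.1 gives deaths alone as 78/1,187 = 6.6%.

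**4. What the planned model would show.** Assume a factor with 20% prevalence, severity risk ratio 3, no effect on infection, rare diagnosis, and severe infections k times as likely to be diagnosed. If s is the severe share among diagnosed cases, the severe share among all infections is q = s/(k - (k - 1)s). Then q0 = q/(0.2 × 3 + 0.8), q1 = 3q0, and

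OR = [1 + (k - 1)q1] / [1 + (k - 1)q0].

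For k = 5 and s = 0.10: q = 0.0217, q0 = 0.0155, q1 = 0.0466, OR = 1.186/1.062 = 1.12. With k = 1 the odds ratio is 1.00 throughout.

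**5. What a severity model could detect.** Wald test of the log odds ratio, n = 500, two-sided 5%, unadjusted, OR 2. Example at 15% severe and 20% factor prevalence: the risks are 13.0% without and 23.0% with the factor, so the variance is 1/23 + 1/77 + 1/52 + 1/348 = 0.0786 and the SE 0.280. Then 0.693/0.280 - 1.96 = 0.51, which is 70% power.

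| Severe | Cases of 500 | Planned model OR, k = 2 | Planned model OR, k = 5 | Power at OR 2, 20% prevalence | OR for 80% power, 20% prevalence | OR for 80% power, 10% prevalence |
|---|---|---|---|---|---|---|
| 10% | 50 | 1.07 | 1.12 | 56% | 2.45 | 2.91 |
| 15% | 75 | 1.11 | 1.18 | 70% | 2.18 | 2.60 |
| 26% | 130 | 1.19 | 1.32 | 83% | 1.95 | 2.36 |
| 27.8% | 139 | 1.21 | 1.34 | 84% | 1.93 | 2.34 |
| 45.2% | 226 | 1.35 | 1.58 | 86% | 1.89 | 2.38 |

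**6. Size of the variable list.** The variables in 7.3.2 come to at least age 4 + sex 1 + obesity 1 + 18 Appendix 1 rows counted once each + 8 HIV terms = 32. That is 50/32 = 1.6 to 226/32 = 7.1 severe cases per term before any selection.

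**The case against.** The charitable reading is that the word severe in 7.3.2 is a slip and an infection analysis was meant. That would reconcile 7.3.2 with 7.1 and the model sentence in 7.3, but objective 2 would then have no analysis at all, so the gap remains.

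A fairer challenge is to the top of the severity range. Section 6.1 reports 436 hospitalisations among 1,187 PLWHIV, or 36.7%. Most components of the composite require hospitalisation. Even if every hospitalised patient were severe and all 78 deaths occurred elsewhere, the rate would be 514/1,187 = 43.3%. So 45% is above what those figures allow, although the enrolled 500 may differ. Capping at 36.7% gives about 184 severe cases, 5.7 per term, 63% non-severe at that end, and an odds ratio of 1.46 for k = 5. Power (86%) and the detectable odds ratio (1.89) at 20% prevalence do not change.

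It is also true that the prevalence, risk ratio and k in the illustration are invented inputs. They show the direction and possible size of the error; the contradiction rests on the text alone.

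**Conclusion.** The concern holds and must be fixed before analysis. Primary objective 2 and the CD4 hypothesis have no specified analysis, and a different analysis carries their label. This follows from the wording of sections 3, 3.1, 5.1, 7.1, 7.3, 7.3.2 and 7.3.3 and needs no assumption.

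The size of the consequence does rest on assumptions. Over 10-45% severe, 55-90% of the modelled cases would be non-severe. A factor that triples severity would appear with an odds ratio between 1.0 and about 1.6 for k from 1 to 5. A correct analysis on 500 cases is feasible for moderate to large effects only.

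A minor related point: sex is a matching variable and cannot be estimated in the conditional model, although it is on the list of factors to assess. Age is matched within 5 years, so little of its effect remains there.

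**What to change.** - Define the second primary analysis among PLWHIV with COVID-19 only, as an unconditional logistic regression of the primary composite (yes/no) on the listed HIV, demographic and comorbidity variables, with age and sex included. Consider adding ethnicity where available: it is collected, but it is not on the 7.3.2 list.
- State its population as all eligible PLWHIV with COVID-19. Section 7.4 restricts analysis to subjects with a match, which this model does not need.
- Restate the AIC and P < 0.20 steps for this model and say in advance how the list will be cut to what the expected events support. Keeping current CD4 count and nadir in regardless of screening would ensure that the section 3 hypothesis is tested.
- State that the figure of 28 parameters applies to the n = 1,500 infection model, and add a precision statement over a range of assumed severity rates, such as the table above.
- Keep the matched conditional logistic model as a separately labelled analysis of factors associated with SARS-CoV-2 diagnosis. Drop sex from its assessed factors and do not interpret age there as a risk factor.

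The cost is protocol and SAP wording, since section 6.2 already lists the components of the composite and the covariates. A change to a primary analysis may need ethics committee review under section 9.1. The statistical price is fewer supportable parameters and lower precision than in the infection model. A Cox version is not proposed, because section 6.2 does not list dates of critical care admission or death.
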